Exclusion criteria	
If any of the following criteria are met, the subject should not be included in the study:
 
 1. Individual with PT and/or PRN serum IgG antibodies ≥ 20 International units/ml (IU/ml). NOTE! One control group with PRN serum IgG antibodies ≥ 20 IU/ml and PT serum IgG antibodies < 20 IU/ml will be included. 2. Vaccinated with the study vaccine in the Child Innovac study (EudraCT number 2010-019936-11). 3. Pregnant or lactating women. Pregnancy not planned and to be avoided during the study by use of effective contraceptive methods. 4. Blood pressure after resting $\geq 150/90$ mm Hg at screening. 5. Heart rate after resting ≥ 80 bpm at screening. 6. Respiratory rate after resting ≥ 20/minute at screening. 7. Unwillingness to refrain from the use of nicotine products from screening through day 28. 8. Use of narcotic drugs and/or a history of drug/alcohol abuse within the past 2 years prior to screening 9. The subject has donated blood or suffered from blood loss of at least 450 ml (1 unit of blood) within 60 days prior to screening or donated plasma within 14 days prior to screening. 10. Receipt of immunoglobulin, blood derived products, systemic corticosteroids or other immunosuppressant drugs within 90 days prior to day 0. 11. Asthma or other chronic respiratory problems. 12. Use of corticosteroids in the respiratory tract (e.g. nasal steroids, inhaled steroids) within 30 days prior to day 0. 13. Receipt of a vaccine within the last 30 days prior to day 0 or planned vaccination within the next 30 days after day 0. 14. Known hypersensitivity to any component of the study vaccine. 15. Current participation in any other clinical trial or participation (and during the whole study) in any clinical trial in the previous 3 months prior to day 0. 16. Inability to adhere to the protocol, including plans to move from the area. 17. Family (first degree) history of congenital or hereditary immunodeficiency. 18. Past or present infection with HIV, hepatitis B or C. 19. Chronic conditions requiring ongoing active medical interventions, such as diabetes mellitus or cardiovascular disease.

Study title	Phase Ib (high dose), double-blind, single centre, dose-escalating, placebo-controlled, randomized study of a live attenuated B. pertussis strain given as a single intranasal dose to healthy adult volunteers
Study Identification Number:	C14-80
Sponsor	INSERM

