- 2) the levels of cytokine after stimulation of PBMC with *B. pertussis* antigens and unrelated antigens.
- 3) the cytokine levels in nasopharyngeal aspirate.

To explore the frequency and magnitude of colonization and as well as antibody, B and T cell responses in a small group of healthy adult volunteers with high PRN antibody levels (only highest vaccine dose).

V. Selection of volunteers

V.1. INCLUSION CRITERIA

Subject will be included in the study if he/she meets all the following criteria:

1. Healthy male or female between 18 and 32 years of age, vaccinated or unvaccinated with acellular pertussis vaccine.
2. Female subject of child bearing potential must be willing to ensure to use one of the following methods of contraception from 2 weeks before vaccination till one month after vaccination to avoid pregnancy during the study:
 - Complete abstinence from penile-vaginal intercourse
 - Double barrier method (male condom/spermicide, male condom/diaphragm, diaphragm/spermicide)
 - Any intrauterine device (IUD) with published data showing that the expected failure rate is <1% per year
 - Approved hormonal contraception (except low-dose gestagen), which is not contraindicated to study vaccine administration
3. Informed consent form (ICF) signed by the subject.
4. Subject shall be able to attend all scheduled visits and to understand and comply with the study procedures.

V.2. EXCLUSION CRITERIA

If any of the following criteria are met, the subject must not be included in the study:

1. Individual with PT and /or PRN serum IgG antibodies ≥ 20 IU/ml. NOTE! One control group with PRN serum IgG antibodies ≥ 20 IU/ml and PT serum IgG antibodies <20 IU/ml will be included.
2. Vaccinated with the study vaccine in the Child Innovac study (EudraCT number 2010-019936-11).
3. Pregnant or lactating women. Pregnancy not planned and to be avoided during the study by use of effective contraceptive methods.
4. Blood pressure after resting $\geq 150/90$ mm Hg at screening.
5. Heart rate after resting ≥ 80 bpm at screening.
6. Respiratory rate after resting ≥ 20 /minute at screening.
7. Unwillingness to refrain from the use of nicotine products from screening through day 28.
8. Use of narcotic drugs and/or a history of drug/alcohol abuse within the past 2 years prior to screening.
9. The subject has donated blood or suffered from blood loss of at least 450 ml (1 unit of blood) within 60 days prior to screening or donated plasma within 14 days prior to screening.

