- Day 2: 2 individuals with at least 4 hours interval
- Day 3: 3 individuals with at least 2 hours interval
- Day 4: 4 individuals with at least 1 hour interval
- Day 5: 5 individuals with at least 1 hour interval

Interim safety meetings with the DSMB for recommendation to the sponsor will be held before administering the next dose. At the interim safety meetings, safety data covering 28-days of post-vaccination follow-up of group 1 and group 2, respectively, will be available. Taking into account the time for the DSMB to meet and to give its recommendations for dose escalation, group 1 volunteers will have been followed up during at least 6 weeks by the time the group 2 volunteers become vaccinated. Likewise, group 2 volunteers will have been followed up during at least 6 weeks by the time the group 3 volunteers become vaccinated.

A non-controlled group (group 4) consisting of 6 individuals will be vaccinated with 10^9 cfu of the organism (open-label) to investigate the frequency of colonization in subjects with high anti-PRN antibody levels (≥ 20 IU/ml) and PT serum IgG antibodies < 20 IU/ml.

VI.3. STUDY VISITS

This study will include 9, or if required, 10 study visits. An overview of all study visits with interviews, clinical examinations and samples to be taken are presented in I.4 "Procedural flow chart".

- Visit 1, recruitment visit 1-6 weeks before vaccination: medical history, physical examination and collection of blood and urine sample and ECG.
- Visit 2, inclusion visit, 1-6 weeks after visit 1: physical examination, collection of blood and urine (females only) sample and vaccination with vaccine or placebo.
- Visit 3, 4 ± 1 days after visit 2: physical examination, safety follow up of vaccination and collection of blood (in the high dose group 3 only) and nasopharyngeal sample.
- Visit 4, 7 ± 1 days after visit 2: physical examination, safety follow up of vaccination and collection of blood and nasopharyngeal sample.
- Visit 5, 11 ± 1 days after visit 2: physical examination, safety follow up of vaccination and nasopharyngeal sample.
- Visit 6, 14 ± 1 days after visit 2: physical examination, safety follow up of vaccination and collection of blood and nasopharyngeal sample.
- Visit 7, 21 ± 1 days after visit 2: physical examination, safety follow up of vaccination and collection of blood and nasopharyngeal sample.

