- Visit 8, 28 (- 1; +7) days after visit 2: physical examination, safety follow up of vaccination and collection of blood, urine (females only) and nasopharyngeal sample.

- Visit 8, 45 (-5; +10) days after visit 2: physical examination, safety follow up of vaccination and collection of nasopharyngeal sample in volunteers in which BPZE1 bacteria were still detectable on day 28 (- 1; +7).
- Visit 9, 6±1 months after visit 2: physical examination, safety follow up of vaccination and collection of blood and nasopharyngeal sample.

VI.3.1. First contact

The clinical trial site will either find the healthy volunteers by the use of Karolinska Trial Alliance database or by advertising in the local periodicals or on Facebook.

All subjects will have a personal contact by phone and a screening visit can be booked.

Written information about the study will be sent to the potentially healthy volunteers before they come to their first visit at the clinic.

VI.3.2. Visit 1, screening 1-6 weeks before vaccination

During this visit the investigator will:

1. Inform the subject about the study and obtain a signed ICF. ICF should be dated and signed by the volunteer and the investigator before any study-related activities take place.
2. Verify the subject's eligibility by reviewing inclusion and exclusion criteria.
3. Assign a unique screening number to the subject (refer to section VI.4. "Screening number and randomization procedure").
4. Collect information regarding the subject's demography. Record the information in the CRF.
5. Collect information regarding the subject's personal and medical history and concomitant treatment as defined in section VII.1. "Prior medications and vaccination". Record the information in the CRF.
6. Perform a full physical examination including ECG and measure
 - a) oral temperature
 - b) blood pressure
 - c) pulse
 - d) respiratory rate
 - e) height
 - f) weightand record the information in the subject's eCRF
7. Collect blood samples as described in section XII.3. "Blood samples". Complete the appropriate document provided in the investigator or delegate Site file.
8. Collect urine samples as described in section XII.5. "Urine samples". Complete the appropriate document provided in the investigator or delegate Site file.

VI.3.3. Visit 2, day 0, vaccination

During this visit the investigator or delegate will:

1. Verify the subject's eligibility by reviewing inclusion and exclusion criteria.

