After the subject's eligibility has been verified and after the ICF has been signed by the subject and by the investigator all subjects will have blood samples collected according to the following schedule for

- Blood cell counts i.e. hematology (haemoglobin, total and differential WBC (i.e. granulocytes: neutrophils, eosinophils, and basophils, non-granulocytes: lymphocytes and monocytes) platelets (thrombocytes) and RBC.
- Blood chemistry
- Pregnancy testing (females only)
- HIV and hepatitis screening
- Pertussis specific humoral and cellular immunity

Blood samples

Study Visit	1	2	3	4	5	6	7	8	9
	1-6 weeks prior to visit 2	Day 0	Day 4±1	Day 7±1	Day 11±1	Day 14±1	Day 21±1	Day 28 -1;+7	Month 6±1
Safety labs:									
Hematology ^a	4 ml	4 ml		4 ml		4 ml		4 ml	4 ml
Blood chemistry ^b	11 ml								
Screening for HIV, hepatitis B and C (no anticoagulant)	3.5 ml								
Serum PT and PRN IgG antibodies (no anticoagulant)	4.5 ml								
Immunogenicity Labs and Sample Archive:									
Binding pertussis IgG/IgA antibodies (no anticoagulant)		9 ml		4.5ml		9 ml	4.5 ml	9 ml	9 ml
Lymphoproliferative response		x	x ^c			x		x	x
Cryo-preserved cells, optional assays (Na-heparin)		x				x		x	x
Volume for cellular immunogenicity (Na-heparin)(ml)		12x8 ml	2x8 ml			12x8 ml		12x8 ml	12x8 ml
TOTAL BLOOD VOLUME APPROXIMATELY (ML)	23	109	16 ^c	8.5		109	4.5	109	109

^(a) Hematology (haemoglobin, total and differential WBC (i.e. granulocytes: neutrophils, eosinophils, and basophils, non-granulocytes: lymphocytes and monocytes) platelets (thrombocytes) and RBC.

^(b) Blood chemistry (potassium, calcium, sodium, creatinin, albumin, serum bilirubin, alkaline phosphatases alaninaminotransferase (ALAT), aspartataminotransferase (ASAT), glutamyltransferase (GT), high sensitive C-reactive protein, blood glucose, thyroid stimulating hormone (TSH), human chorionic gonadotropin (hCG) (females only).

^(c) Blood will only be collected from the high dose group 3 subjects (n=16).

The blood sample should be drawn using aseptic techniques (see detailed procedure in the investigator's file). Blood must be collected in tubes with or without anticoagulant as indicated.

Blood samples transport

The blood samples for safety analysis should be transported to the department of Lab Medicine at the Karolinska University Hospital, Solna.

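### Exclusion 9 covers blood and plasma donation only up to screening, so a full-unit donation in the 1 to 6 weeks before Day 0 does not meet it, although dosing starts a schedule that draws about 340 mL in 28 days.

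*Combined protocol and SAP*

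**What the plan says.** Exclusion 9 has the same wording in the protocol synopsis (I.3), protocol V.2 and SAP 3.1.1: it excludes a volunteer with a blood donation or "blood loss of at least 450 ml (1 unit of blood) within 60 days prior to screening". Plasma has its own limit: "donated plasma within 14 days prior to screening". Both windows close at Visit 1.

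Protocol VI.3 places dosing later: "Visit 2, inclusion visit, 1-6 weeks after visit 1". At Visit 2 the investigator is told to repeat the check (VI.3.3): "Verify the subject's eligibility by reviewing inclusion and exclusion criteria".

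Several nearby criteria count back from dosing instead. Exclusion 10 covers "systemic corticosteroids or other immunosuppressant drugs within 90 days prior to day 0" and exclusion 13 covers "Receipt of a vaccine within the last 30 days prior to day 0"; exclusions 12 and 15 also use Day 0. Exclusions 4, 5, 6 and 8 are tied to screening, and exclusion 7 runs from screening to Day 28.

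Blood volumes per visit are tabulated in I.4 and again in XII.3.

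**The concern.** A criterion on recent donation in a trial with heavy blood sampling should hold on the day when that sampling begins. This one stops 7 to 42 days earlier. Repeating the check at Visit 2 does not close the gap, because the wording still points back to Visit 1.

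Two things are at stake. The first is volunteer welfare: a recently bled person could enter a schedule whose first large draw is on Day 0 itself. The second is the haematology baseline. Haemoglobin and red-cell counts are among the safety assessments listed in protocol IV.1. SAP 2.3.2 calculates change from D00, and SAP 3.5.1 describes the counts by group, allocation and visit. A Day 0 value taken soon after a donation is not a steady-state baseline.

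**Working it through.** **1. Reproduce the tabulated volumes (XII.3).**
- Visit 1: 4 + 11 + 3.5 + 4.5 = 23 mL
- Visits 2, 6, 8 and 9: 4 + 9 + 12 × 8 = 109 mL each
- Visit 3, Group 3 only: 2 × 8 = 16 mL
- Visit 4: 4 + 4.5 = 8.5 mL
- Visit 7: 4.5 mL

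All agree with the stated totals. The documents give no 28-day sum.

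**2. Sum Day 0 to Day 28 (Visits 2, 4, 6, 7 and 8).**
- Groups 1, 2 and 4: 109 + 8.5 + 109 + 4.5 + 109 = 340 mL
- Group 3: 340 + 16 = 356 mL

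The 109 mL drawn on Day 0 is included; the 23 mL at screening is not.

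**3. Add one donation of exactly 450 mL in the gap.**
- 450 + 340 = 790 mL; in Group 3, 450 + 356 = 806 mL
- Given the day before dosing, this falls within 1 + 28 = 29 days
- Given just after screening at six weeks before dosing, it spreads over about 42 + 28 = 70 days

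**4. What the present windows cover when screening is at Day −42.**
- Blood: Day −102 to Day −42 (42 + 60 = 102)
- Plasma: Day −56 to Day −42 (42 + 14 = 56)
- Neither covers the time after Day −42

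A volunteer who gave blood 59 days before screening is excluded, although 59 + 42 = 101 days will have passed by Day 0. One who gave blood the day before dosing is not excluded.

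**5. What a plain switch of anchor to Day 0 would do, with the same screening day.**
- Blood: Day −60 to Day 0. A donation at Day −61, which is 19 days before screening and excluded now, would become allowed.
- Plasma: Day −14 to Day 0. A donation the day before screening (Day −43) would become allowed.

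The screening haematology, chemistry and PT/PRN IgG results that decide eligibility would then lose the cover they have now.

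**6. Look for another rule that closes the gap.**
- V.3 (temporary contraindications): febrile illness and upper respiratory conditions only.
- VII.1: medicines, blood products received and vaccines, not blood given.
- Exclusion 22: rests on laboratory values. Screening samples precede a donation in the gap, Visit 2 haematology is drawn on Day 0, and nothing requires its result before vaccination.
- Exclusion 21: investigator's opinion about a medical condition; donation is not named.
- SAP 3.1.1: no additional statistician check against criterion 9.

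**The case against.** The best defence is that the anchor is deliberate. The text is identical in three places, and exclusions 4, 5, 6 and 8 are also fixed at screening. A reader might infer from the Day 0 criteria that the protocol contradicts itself. It does not: the two anchors coexist, and this is a gap in cover.

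A reader might also infer that nothing could stop a recent donor from being dosed. That goes too far. Visit 2 includes a limited physical examination and vital signs, the volunteer must be healthy, and exclusion 21 leaves room for judgement. Blood loss from illness or injury could well be noticed. A routine voluntary donation is less clearly caught, and no question prompts for it. The consent pages were not available, so an instruction there against donating cannot be ruled out.

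The most tempting stronger reading is that a donor's haemoglobin would start low and climb, and could be mistaken for a vaccine effect. The documents do not support a direction. Before the Visit 8 sample the trial itself removes 109 + 8.5 + 109 + 4.5 = 231 mL (247 mL in Group 3), which works against a rise. Haematology is descriptive, within-group tests are optional, and placebo recipients in each dose group follow the same sampling schedule. What stands is only that the baseline would be disturbed.

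Finally, 790 mL is a worst case, and the documents give no donation rate from which to judge how often it would occur.

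**Conclusion.** The gap is real and the arithmetic reproduces. As worded, exclusion 9 does not apply to a donation of 450 mL or more between screening and Day 0. The worst-case total through Day 28 is 790 mL, or 806 mL in Group 3. One such volunteer would be 1/12 (8%) of an active arm in Groups 1 to 3; that is a share of the data, not an estimate of frequency or bias.

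The conclusion assumes a single donation of exactly 450 mL, the tabulated volumes drawn in full, and no donation instruction in the consent material. That few volunteers would be affected is a judgement, because the documents offer no figure. The primary endpoint and the sample size are untouched. This is a minor point, worth making because the correction is cheap and protects volunteers.

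**What to change.** Extend the windows; do not move them. In the synopsis, V.2 and SAP 3.1.1, keep the sponsor's 60-day limit for blood and 14-day limit for plasma before screening, and add to each: *or at any time between screening and Day 0*. Add a question on donation and blood loss to Visit 2, asked before the blood draw. In VI.3.3 the draw comes before a vial number is assigned, so a volunteer stopped at that point does not disturb the randomisation sequence.

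The cost is one phrase in three places and one question at an existing visit. Occasionally a volunteer will be rescheduled or replaced before dosing. Because the added interval starts at screening, rescheduling would mean a new screening visit; moving Visit 2 alone would not clear the criterion.
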